5.1 Determination of Sample Size

A total of approximately 100 subjects will be randomly assigned to 1 of 2 arms and treated with either sorafenib + placebo or the 2-agent combination of sorafenib + mapatumumab 30 mg/kg in a 1:1 ratio. A sample size of 50 subjects randomized and treated in each group is sufficient to estimate the median time to progression (TTP) with a precision of approximately -1.9 months to +2.6 months relative to the observed median. In addition, a sample size of 50 patients per arm will provide 80% power to detect an improvement in TTP from 5.5 to 8.9 months with at a one-sided significance level of 0.10.

6 Study Subjects

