- Frequency and severity of treatment-emergent adverse events.
- Laboratory parameters.

- Serum mapatumumab concentrations for use in a population pharmacokinetic analysis.

Statistical Methods:

Sample Size:

A total of approximately 100 subjects will be randomly assigned to 1 of 2 arms and treated with either sorafenib + placebo or the 2-agent combination of sorafenib and mapatumumab at 30 mg/kg in a 1:1 ratio. A sample size of 50 subjects randomized and treated in each group is sufficient to estimate the median time to progression with a precision of approximately -1.9 M to +2.6 M relative to the observed median. In addition, a sample size of 50 patients per arm will provide 80% power to detect an improvement in TTP from 5.5 to 8.9 M with at a one-sided significance level of 0.10.

Statistical Analysis:

The primary analysis will be an estimate of median time to progression in each arm using Kaplan Meier methods, reported with 95% confidence intervals, along with testing the hazard ratio for time to progression at a 1-sided significance level of 0.10 with a Cox proportional hazards model controlling for the factors stratifying the randomization as covariates. Secondary analyses include estimates, using Kaplan Meier methods, of median progression-free survival (PFS) and median overall survival (OS) along with associated logrank testing. In addition, estimates of overall response rate (CR+PR) and disease control rate (CR+PR+SD) will be reported with 95% confidence intervals and an estimate of the difference in response rates and disease control rates between groups will be reported and tested for significance with a Pearson chi-square test (or Fisher's exact test). For frequency and severity of adverse events and laboratory toxicity grading, counts and rates will be presented.

AM01
21Dec10

Study Calendar:

The study calendar is located in Section [6.3](#) of the protocol.

Table of Contents

Revision Chronology for HGS1012-C1103 (200149).....	2
Study Synopsis	4
Table of Contents.....	11
List of Tables	14
List of Abbreviations	15
1 Background.....	17
1.1 Hepatocellular Carcinoma	17
1.2 Treatment Options for Patients with Hepatocellular Carcinoma.....	17
1.3 The Role of the TRAIL Pathway in HCC	17
1.3.1 TRAIL and TRAIL Receptors	17
1.3.2 TRAIL and HBV/HCV Infection	18
1.4 Mapatumumab	18
1.4.1 Mapatumumab Pharmacology	18
1.4.2 Non-Clinical Mapatumumab Safety Studies	19
1.4.3 Clinical Experience with Mapatumumab	20

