Sorafenib is the standard of care for treatment of patients with advanced hepatocellular carcinoma. Sorafenib is a multikinase inhibitor that targets the Raf/mitogen-activated protein kinase/extracellular signal-regulated kinase signaling pathway, blocks tumor angiogenesis and induces apoptosis (Panka et al, 2006; Rahmani et al, 2005; Yu et al, 2005; Wilhelm et al, 2004). Sorafenib was approved by the European Medicines Agency and the Food and Drug Administration in 2007 for treatment of patients with hepatocellular carcinoma based on the demonstration of improved overall survival in the 602 patient randomized, placebo-controlled, Phase 3 “Sorafenib Hepatocellular Carcinoma Assessment Randomized Protocol” (SHARP) trial. Approximately half the 602 patients had either hepatitis C virus or hepatitis B virus as underlying etiology and 26% had alcohol-related cirrhosis. The median overall survival was 10.7 months for patients in the sorafenib arm compared with 7.0 months for patients in the placebo arm (hazard ratio in the sorafenib group, 0.69 95% confidence interval, 0.55 to 0.87; $p < 0.001$). The median time to radiologic progression was 5.5 months in the sorafenib arm, compared with 2.8 months in the placebo arm ($p < 0.0001$) (Llovet et al, 2008). Seven patients in the sorafenib group (2%) and 2 patients in the placebo group (1%) had a PR; no patients had a CR.

A 2nd randomized, placebo-controlled Phase 3 trial was conducted in the Asia-Pacific region (Cheng et al, 2009). The 226 patients randomly assigned to sorafenib or placebo in this trial appeared to have more advanced disease than those in the SHARP trial, with a higher frequency of extrahepatic spread, poorer ECOG PS, and higher levels of AFP, but still showed a benefit from treatment with sorafenib. The majority (73%) had hepatitis B virus as an underlying etiology. The median overall survival was 6.5 months for patients in the sorafenib arm, compared with 4.2 months in the placebo group (hazard ratio, 0.68, 95% confidence interval, 0.50-0.93; $p = 0.014$). The median time to progression was 2.8 months in the sorafenib group, compared with 1.4 months in the placebo group (hazard ratio, 0.57, 95% confidence interval 0.42-0.79; $p = 0.0005$).

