9.2 Sample Size Rationale

A total of approximately 100 subjects will be randomly assigned to 1 of 2 arms and treated with either sorafenib + placebo or the 2-agent combination of sorafenib and mapatumumab at 30 mg/kg in a 1:1 ratio. A sample size of 50 subjects randomized and treated in each group is sufficient to estimate the median time to progression with a precision of approximately -1.9 M to +2.6 M relative to the observed median. In addition, a sample size of 50 patients per arm will provide 80% power to detect an improvement in TTP from 5.5 to 8.9 M with at a one-sided significance level of 0.10.

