7.1.2 Primary Efficacy Analyses

The primary analysis will be an estimate of median TTP in each arm using Kaplan Meier methods, reported with 95% confidence intervals, along with testing the hazard ratio for TTP at a 1-sided significance level of 0.10 with a Cox proportional hazards model controlling for the factors stratifying the randomization as covariates.

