7.3.2 Other Censoring Rules

Subjects who reach the survival endpoint due to any reason prior to experiencing a radiologic disease progression will be censored for TTP at the date of their last complete disease assessment. Subjects remaining on study without radiologic disease progression or death at the time of analysis will be censored for TTP and PFS at the date of their last

complete disease assessment. Subjects lost to follow-up prior to experiencing a radiologic disease progression or death will be censored for TTP and PFS at the date of their last complete disease assessment.

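### One precision (-1.9 to +2.6 months) is stated for the median TTP in both arms, but at the planned 8.9-month mapatumumab median it is about -3.1 to +4.2 months

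*SAP*

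**What the plan says.** SAP 5.1 gives two justifications for 50 subjects per group. The first is precision: that number is "sufficient to estimate the median time to progression (TTP) with a precision of approximately -1.9 months to +2.6 months relative to the observed median". The second is power: "80% power to detect an improvement in TTP from 5.5 to 8.9 months" at a one-sided level of 0.10.

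The precision statement also stands in Protocol 9.2 ("with a precision of approximately -1.9 M to +2.6 M relative to the observed median") and in the sample size paragraph of the protocol synopsis ("sufficient to estimate the median time to progression with a precision of approximately -1.9 M to +2.6 M"). In all three places it covers each group, and no median, confidence level, distribution, censoring assumption or interval method is attached to it.

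Two other sections bear on the figure. Protocol 1.5 supplies the likely source of the control value when it describes the earlier Phase 3 trial: "The median time to radiologic progression was 5.5 months in the sorafenib arm". SAP 7.1.2 makes the same quantity part of the primary analysis: "an estimate of median TTP in each arm using Kaplan Meier methods, reported with 95% confidence intervals".

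**The concern.** Stated relative to the observed median, the offsets read as something to place around whatever median is seen, in either arm. That cannot be right for both arms if the trial goes as planned. For exponential times the interval is proportional to the median, and 8.9/5.5 = 1.62, so an offset that is right at 5.5 months is too narrow by that factor at 8.9.

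The per-arm median with its 95% interval belongs to the primary analysis. A reader who applies the stated offsets to an observed median of 8.9 months expects an interval of 8.9 - 1.9 = 7.0 to 8.9 + 2.6 = 11.5 months, with a lower limit 1.5 months above the 5.5-month planning value. If the true interval is much wider, the mapatumumab median says less on its own than the plan suggests.

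**Working it through.** **Inputs.** n = 50 per arm, medians 5.5 and 8.9 months, stated offsets -1.9/+2.6 (SAP 5.1); 95% level and Kaplan-Meier estimation (SAP 7.1.2). Assumptions not in the documents: exponential TTP and, at first, no censoring before the interval bounds.

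**Reproducing the stated figure.** Invert the survival curve at the median with the variance fixed at its value there.

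- Half-width on the survival scale: 1.96 × sqrt(0.25/50) = 0.139, so the bounds fall where S = 0.639 and S = 0.361.
- Time at S for an exponential curve with median m: t = m × log2(1/S). This gives 0.647m and 1.468m.
- m = 5.5: 3.56 and 8.08 months, or -1.94/+2.58. This rounds to the stated pair; the width is 4.5 months.

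**Same method at the other planned median.**

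- m = 8.9: 5.76 and 13.07 months, or -3.14/+4.17. The width is 7.3 months.

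By this method the width at 8.9 months is 7.31 with n = 50 and falls to 4.49 only with n = 128 per arm (illustration only).

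**Does the result depend on the method?** Other intervals with n = 50 and no censoring, at 95% except where noted:

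| Method | Median 5.5 | Median 8.9 |
|---|---|---|
| Linear, variance S(1-S)/n at each time | -1.88/+2.47 | -3.04/+3.99 |
| Log-log | -2.07/+2.41 | -3.35/+3.90 |
| Log-time delta method | -1.81/+2.70 | -2.93/+4.38 |
| Order statistics 18 and 33 (96.7% coverage) | -2.00/+2.91 | -3.24/+4.71 |
| Parametric exponential, 50 events: m × exp(±1.96/sqrt(50)) | -1.33/+1.76 | -2.15/+2.84 |

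The parametric interval with every subject progressed is the most favourable of these, and at 8.9 months it is still wider than stated on both sides. It is also not the Kaplan-Meier interval that SAP 7.1.2 specifies.

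**Is 5.5 months the only basis for the stated pair?** No. Parametric exponential intervals give -1.89/+2.58 at 7.0 months with 39 events and -1.94/+2.56 at 8.0 months with 50 events. The documents cannot separate these.

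**Censoring.** Under SAP 7.3.2, subjects who die "prior to experiencing a radiologic disease progression will be censored for TTP at the date of their last complete disease assessment", so some censoring is certain, but no rate is given. Simulated Kaplan-Meier intervals (4,000 trials per setting, independent exponential censoring; medians across trials of bound minus observed median), assuming 0% to 30% of subjects censored before progression:

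| Interval | Median | 0% censored | 30% censored |
|---|---|---|---|
| Log-log | 5.5 | -1.9/+2.4 | -2.0/+2.6 |
| Log-log | 8.9 | -3.0/+3.9 | -3.3/+4.3 |
| Linear | 8.9 | -2.5/+3.9 | -3.0/+4.3 |

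Repeat runs differ by about 0.1 month.

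**The case against.** The strongest reply is that nothing has been miscalculated. The stated pair reproduces at the control median, the text says the figure is approximate, and the 95% level and Kaplan-Meier method can be read across from SAP 7.1.2. On this view the plan has only left an assumption unlabelled. The reply adds that the basis is not identifiable. For example, the midpoint of the two planned medians, (5.5 + 8.9)/2 = 7.2 months, with 40 events per arm gives -1.92/+2.62 by the parametric formula. Forty per arm is 80 in total, close to the 78 (Schoenfeld) or 81 (Freedman) events that the power statement needs. One figure for both arms would then be an average design value. Finally, the reported interval will come from the data, and no decision rule uses the planned precision.

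Much of this stands. The sponsor's basis is unknown, the level and method are missing only from the precision statement itself, and the practical effect is small. It is also fair that -3.1/+4.2 is a large-sample approximation: uncensored simulated Kaplan-Meier intervals at 8.9 months are somewhat narrower, chiefly on the lower side.

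It does not rescue the statement. The 7.2-month basis is parametric, which does not match the planned analysis, and by its own formula it gives -2.37/+3.23 at 8.9 months, a width of 5.6 against the stated 4.5. An average across the arms is not what the text claims, since it attaches the offsets to each group and to the observed median.

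**Conclusion.** The concern holds. The stated precision fits a median near 5.5 months. At the 8.9 months planned for mapatumumab, the matching interval is about -3.1/+4.2 months, that is about 5.8 to 13.1 instead of 7.0 to 11.5, with a lower limit that only just clears 5.5. Simulated Kaplan-Meier intervals at 8.9 months run from about -2.5/+3.9 to -3.3/+4.3 over 0% to 30% censoring, so the direction and rough size do not depend on the exact method.

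The figures rest on exponential TTP and an assumed censoring range. That 5.5 months was the sponsor's basis is inferred. The finding that the pair is too narrow at 8.9 months does not need that inference. The effect is confined to this one stated property of the design. The power statement is separate and consistent: 78 to 81 events are needed, which 100 subjects can supply. The point should be corrected, but it does not threaten the trial's conclusions.

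**What to change.** Replace the precision sentence in SAP 5.1, Protocol 9.2 and the synopsis with wording such as:

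> With 50 subjects per group, the 95% nonparametric (Kaplan-Meier type) confidence interval for the median TTP is expected, as a planning approximation, to extend from about -1.9 to +2.6 months around a median of 5.5 months and from about -3.1 to +4.2 months around a median of 8.9 months. This assumes exponential TTP and no censoring before the interval bounds; censoring tends to widen the intervals.

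If the sponsor derived -1.9/+2.6 from another median, level or method, it should state that basis instead and give the corresponding figure for both planned medians.

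The cost is one sentence in three places and a less favourable stated figure for the mapatumumab arm. Sample size, power and the primary Cox test stay as they are.

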6.1 Subject Disposition

Subject eligibility, compliance, and study completion will be summarized. Reasons for failing screening, failing enrollment (randomized but never received treatment) or not completing the study (as defined in Section 6.3 below) will be identified.

6.2 Extent of Exposure

The extent of exposure to mapatumumab/placebo and to sorafenib will be assessed by examining duration of exposure in both months and cycles (cycles only relevant while subject is administered mapatumumab/placebo), dose intensity, relative dose intensity, dose reductions, dose omissions and dose delays by treatment group.

Duration of exposure for mapatumumab/placebo will be calculated as the date of dosing for the last cycle plus 21 days minus the date of 1st treatment. For subjects who die prior to Day 21 of the last cycle, duration of exposure will be calculated as the date of death

minus the date of 1st treatment plus 1 day. Duration of exposure for sorafenib will be calculated as the date of last dose minus the date of 1st treatment plus 1 day.

Cumulative dose received for mapatumumab will be calculated as

$$\text{Cumulative dose received} = \sum_{k=1}^K \text{Dose received at each cycle (mg/kg)}$$

where K = total number of treatment cycles received by the subject. In the case that body weight is unknown at a visit, the last non-missing measurement prior to the visit will be used.

Cumulative dose received for sorafenib will be calculated as

$$\text{Cumulative dose received} = \sum_{m=1}^M \text{Dose received each day (mg)}$$

where M = total number of days the subject received sorafenib.

Dose intensity will be expressed as the cumulative dose for mapatumumab (mg/kg) and sorafenib (mg) received, respectively, divided by duration of treatment (weeks) for each treatment, respectively.

$$\text{Dose intensity} = \frac{\text{Cumulative dose received (mg/kg or mg)}}{\text{Duration of treatment (weeks)}}$$

such that the definition of duration of treatment is dependent on the order of treatment discontinuation. If both mapatumumab and sorafenib are discontinued on the same date the duration of treatment for mapatumumab is defined as the date of dosing of mapatumumab in the last cycle plus 21 days minus the date of 1st treatment and the duration of treatment for sorafenib is defined as the date of last dose of sorafenib minus the date of 1st treatment plus 1 day. If mapatumumab is discontinued prior to sorafenib the duration of treatment for mapatumumab is defined as either the date of dosing of mapatumumab for the last cycle plus 21 days minus the date of 1st treatment, or the date of last dose of sorafenib minus the date of 1st treatment plus 1 day, whichever is greater. Duration of treatment for sorafenib will not differ from when both mapatumumab and sorafenib are discontinued on the same date. If sorafenib is discontinued prior to mapatumumab the duration of treatment for sorafenib is defined as the date of dosing of mapatumumab in the last cycle minus the date of 1st treatment plus 1 day. Duration of

treatment for mapatumumab will not differ from when both mapatumumab and sorafenib are discontinued on the same date.

Relative dose intensity will be expressed as the ratio of dose intensity and planned dose intensity

$$\text{Relative dose intensity} = \frac{\text{Dose intensity (mg/kg/weeks or mg/weeks)}}{\text{Planned dose intensity (mg/kg/weeks or mg/weeks)}}$$

such that planned dose intensity for mapatumumab is equal to the planned dose (mg/kg) divided by the number of weeks within a cycle and planned dose intensity for sorafenib is 800 mg times the duration of exposure to sorafenib in days divided by the number of weeks on treatment.

Mapatumumab/placebo doses that are administered 2 or more days from the target date of dosing will be considered delayed. The target date of dosing for each cycle is the previous date of dosing plus 21 days. The length of delay for a delayed dose is calculated as the actual date of dosing minus the target date of dosing. Descriptive statistics will be provided by treatment group.

Dose reductions are not permitted for mapatumumab/placebo. However, any mapatumumab/placebo dosing interruptions that take place resulting in a reduction from the intended dose will be considered dose reductions. Sorafenib dose reductions will be summarized. A dose reduction will be defined as a physician decision to reduce the prescribed dose to a lower level relative to the previous prescribed dose while on treatment (including reductions to 0 mg which would constitute dose omission, also analyzed separately, see below). The number of subjects requiring at least 1 dose reduction will be summarized along with the maximum dose level reduction attained for each subject. In addition, rates of subjects requiring dose reductions due to adverse events (AEs) or laboratory abnormalities will be provided. Statistical analysis of dose reduction rates will include Pearson chi-square testing (or Fisher's exact testing, as appropriate) for differences between groups. Dosing errors for either mapatumumab/placebo or sorafenib will not be identified as dose reductions in the analysis.

In addition, all sorafenib dose reductions observed (possibly multiple events per subject) will be summarized by treatment group and reason. The percent of dose reductions that resulted in an eventual return to the original dose level from which the subject was reduced will be calculated.

The number of subjects requiring sorafenib dose omissions will be summarized by treatment group. A subject will be determined to have a dose omission if the prescribed dose for a given time interval (while on sorafenib treatment) is 0 tablets per day. Statistical analysis of the rate of subjects requiring dose omission (overall, due to AEs,

and due to laboratory abnormalities) will include Pearson chi-square testing (or Fisher's exact testing, as appropriate). In addition, all dose omissions (possibly multiple events per subject) will be summarized by treatment group and reason.

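### When sorafenib stops first, SAP 6.2 ends its dose-intensity denominator 20 days before mapatumumab's in the same subject

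*SAP*

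**What the plan says.** SAP 6.2 (Extent of Exposure) defines dose intensity as cumulative dose "divided by duration of treatment (weeks) for each treatment, respectively". It lists "dose intensity, relative dose intensity, dose reductions, dose omissions and dose delays by treatment group" as outputs, so absolute and relative dose intensity are separate measures. Duration of treatment then depends on the order of discontinuation.

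- **Both agents stopped on the same date.** Mapatumumab: "the date of dosing of mapatumumab in the last cycle plus 21 days minus the date of 1st treatment". Sorafenib: first treatment to its own last dose, inclusive.
- **Mapatumumab stopped first.** Mapatumumab takes its own cycle end "or the date of last dose of sorafenib minus the date of 1st treatment plus 1 day, whichever is greater". Sorafenib is as in the same-date case.
- **Sorafenib stopped first.** Sorafenib: "the date of dosing of mapatumumab in the last cycle minus the date of 1st treatment plus 1 day". For mapatumumab, the duration of "treatment for mapatumumab will not differ from when both mapatumumab and sorafenib are discontinued on the same date".

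Duration of exposure is a separate quantity: "Duration of exposure for sorafenib will be calculated as the date of last dose minus the date of 1st treatment plus 1 day". SAP 4 and 6.3 allow a subject to stop one agent and stay on the other, so the sorafenib-first case is expected to occur.

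**The concern.** The sorafenib-first rule is the odd one out. The inclusive-day form suits the last dose of a drug taken every day. Here it is applied to the dosing date of a drug given every 21 days, which SAP 6.2 otherwise treats as covering 21 days. The rule also lacks the greater-of clause that protects the mapatumumab-first case.

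A shorter denominator raises mg per week, and it does so in subjects who gave up sorafenib while staying on mapatumumab/placebo. Absolute dose intensity is the intensity measure that can show early stopping of sorafenib. Planned sorafenib intensity is built on sorafenib's own exposure days, so relative dose intensity does not fall when sorafenib is simply stopped early.

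**Working it through.** The plan gives no numerical dose-intensity figure to reproduce, so the check is arithmetic on the definitions in SAP 6.2.

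**Inputs.** F = date of first treatment; L = last mapatumumab dosing date; S = last sorafenib dose. The cycle is 21 days and planned sorafenib is 400 mg twice daily (SAP 4), so full dose is 800 × 7 = 5,600 mg/week. Assumptions: mapatumumab given exactly every 21 days, sorafenib taken at 800 mg/day until stopped.

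**Step 1: the denominators when sorafenib stops first.**
- Sorafenib: L − F + 1 days.
- Mapatumumab: L + 21 − F days.
- Difference: 20 days, whatever the length of treatment.

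**Step 2: the other two cases.**
- Mapatumumab first, with sorafenib continuing past the cycle end: both denominators are S − F + 1, so they are equal.
- Same date, with sorafenib taken through Day 21 of the last cycle: S = L + 20, so S − F + 1 = L + 21 − F. They are again equal.

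**Step 3: size per subject.** With c on-schedule mapatumumab cycles, L − F = 21(c − 1). The SAP denominator is 21c − 20 days, the cycle-end denominator is 21c, and the excess is 20/(21c − 20).

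| Cycles | SAP days | Cycle-end days | Ratio |
|---|---|---|---|
| 2 | 22 | 42 | 1.91 |
| 4 | 64 | 84 | 1.31 |
| 6 | 106 | 126 | 1.19 |
| 10 | 190 | 210 | 1.11 |
| 12 | 232 | 252 | 1.09 |

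**Step 4: worked subjects.**
- *Six cycles, sorafenib for 105 days (through cycle 5).* Cumulative dose 105 × 800 = 84,000 mg. SAP: 84,000/(106/7) = 5,547 mg/week. To cycle end: 84,000/(126/7) = 4,667. Under the SAP rule, a full cycle without sorafenib almost disappears.
- *Six cycles, sorafenib for 42 days.* Cumulative dose 33,600 mg. SAP: 33,600/(106/7) = 2,219. To cycle end: 33,600/(126/7) = 1,867.
- *Four cycles, discontinuation dated by the decision to stop.* Both agents stopped on day 84: 84 days, 67,200 mg, 67,200/12 = 5,600 mg/week. Sorafenib stopped on day 83, and so classed as first: 64 days, 66,400 mg, 66,400/(64/7) = 7,263 mg/week. That is above full planned dose, because the 64-day denominator is shorter than the 83 days of exposure. To cycle end: 66,400/12 = 5,533.

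**Step 5: relative dose intensity.** Let D be duration of treatment in days and E sorafenib exposure days. Planned intensity is 800 × E divided by *weeks on treatment*. If that term means D/7, then relative dose intensity = [cumulative dose/(D/7)] / [800E/(D/7)] = cumulative dose/(800E). D cancels. It does not cancel in absolute dose intensity.

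**The case against.** The strongest reply is that this is a convention and not an error. Every sorafenib duration in SAP 6.2 has the inclusive last-dose form, and the sorafenib-first rule keeps it, extending it to the last dose of whichever agent remains. Unequal denominators also arise in the same-date case if both agents stop before the cycle end. And a cycle-end rule can make its own jump. With 4 cycles, the last mapatumumab dose is on day 64. If discontinuation is dated by last dose, stopping both agents on day 64 gives sorafenib 64 days, while stopping sorafenib on day 63 gives 84 days under a cycle-end rule. Intensity is then 63 × 800/12 = 4,200 mg/week, against 5,513 under the current rule.

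Part of this stands. The excess is measured against the convention that the SAP applies to mapatumumab, and the SAP does not say that sorafenib must follow it. Values above 5,600 mg/week cannot arise if discontinuation is dated by last dose. But on that dating a daily drug and a 21-day drug would almost never stop on the same date, which is the case the SAP takes as its base. Dated by the decision to stop, it is the current rule that jumps, from 5,600 to 7,263 mg/week for one day less of sorafenib. The SAP does not say which dating applies, and that is itself part of the gap.

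A reader might also infer that the rule undermines the trial's judgement of whether mapatumumab compromises sorafenib delivery. The documents do not support that. They nowhere give dose intensity that role. The between-arm exposure tests in SAP 6.2 concern dose-reduction and dose-omission rates, and none is planned for dose intensity. Nor is early stopping hidden in general: the 42-day subject shows 2,219 mg/week under the current rule, far below 5,600, and duration of exposure is reported separately.

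**Conclusion.** The point holds as an inconsistency in one descriptive exposure measure. In subjects who stop sorafenib first, the sorafenib denominator is 20 days shorter than mapatumumab's. Absolute sorafenib dose intensity is then higher than on the cycle-end convention by about 31% at 4 cycles, 19% at 6 and 11% at 10, assuming on-schedule dosing. It can exceed full planned dose if sorafenib stops within the last mapatumumab cycle and is classed as first.

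The arm-level effect depends on a proportion that the documents do not give. For illustration, suppose 10% to 30% of an arm stopped sorafenib first. If all had the 42-day profile (excess 2,219 − 1,867 = 352 mg/week), the arm mean would move by 35 to 106 mg/week, or 0.6% to 1.9% of 5,600. If all had the 105-day profile (excess 5,547 − 4,667 = 880), it would move by 88 to 264 mg/week, or 1.6% to 4.7%.

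A reader might infer a bias between arms. The same rule applies to both, so a difference would arise only if the number or timing of sorafenib-first stops differed by arm, and nothing in the documents shows that. TTP, power and duration of exposure are untouched. So is relative dose intensity, provided *weeks on treatment* means duration of treatment. This is a minor correction, worth making before the exposure tables are programmed.

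**What to change.** For subjects who stop sorafenib first, define sorafenib's duration of treatment as the greater of:

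- L + 21 − F (the end point already used for mapatumumab), and
- S − F + 1 (sorafenib's own last dose).

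Truncate it at death in the way SAP 6.2 already does for mapatumumab duration of exposure, so that days after death are not counted. In the same edit, state how the discontinuation date of each agent is determined and what *weeks on treatment* means in planned dose intensity. The 83-day, 4-cycle subject then has max(84, 83) = 84 days and 5,533 mg/week.

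The cost is one line of SAP wording and programming, plus the definitions. No treatment rule or data collection changes.
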